### Oxygen Use

Oxygen use measured as blood oxygen saturation (SpO2) and oxygen flow rate (liters per minute, lpm) will be recorded at every visit from baseline to Day 5.

### Intubation/Extubation

Date and time of intubation/extubation and days on ventilator will be recorded at hospital discharge, Days 28 and 60, as applicable. Proportion of participants who progress to respiratory failure (i.e., need for mechanical ventilation, ECMO, non-invasive ventilation, or high-flow nasal cannula oxygen) will be evaluated.

### Discontinuation of Mechanical Ventilation

If a patient is required to be mechanically ventilated, discontinuation of mechanical ventilator weaning and assessment of readiness for extubation will follow guidance adapted from the National Institutes of Health (NIH) NHLBI ARDS Clinical Network Mechanical Ventilation Protocol Summary ([http://www.ardsnet.org/files/ventilator\\_protocol\\_2008-07.pdf](http://www.ardsnet.org/files/ventilator_protocol_2008-07.pdf)) with additional guidance from the October 2016 American Thoracic Society/American College of Chest Physicians Clinical Practice Guideline: Liberation from Mechanical Ventilation in Critically Ill Adults (<https://www.atsjournals.org/doi/full/10.1164/rccm.201610-2076ST>). These guidelines should be considered as appropriate in the best interest of subjects based on each subject's individual clinical circumstances and the best judgement of their treating clinical care teams as follows:

- A. Conduct a spontaneous breathing trial daily when:
  1. FiO2 ≤ 0.40 and PEEP ≤ 8 OR FiO2 < 0.50 and PEEP ≤ 5.
  2. Patient has acceptable spontaneous breathing efforts. (May decrease vent rate by 50% for 5 minutes to detect effort.)
  3. No neuromuscular blocking agents or blockade.
- B. Spontaneous breathing trial: If above criteria are met and subject has been in the study for at least 12 hours, initiate a trial of up to 120 minutes of spontaneous breathing with FiO2 ≤ 0.5 and PEEP ≤ 5:
  1. Place on T-piece, trach collar, or CPAP ≤ 5 cm H2O with PS ≤ 8 cm H2O
  2. Assess for tolerance as below for up to two hours.
    - a) SpO2 ≥ 90: and/or PaO2 ≥ 60 mmHg
    - b) Spontaneous VT ≥ 4 ml/kg PBW
    - c) RR ≤ 35/min
    - d) pH ≥ 7.3
    - e) No respiratory distress (distress = 2 or more)
      - (1) HR > 120% of baseline
        - o Marked accessory muscle use
        - o Abdominal paradox
        - o Diaphoresis
        - o Marked dyspnea
  3. If not tolerated resume pre-weaning settings.
  4. If tolerated for at least 30 minutes, consider extubation.

### Vital Signs

Vital signs will be collected daily within 30 minutes of the first treatment of the day and at follow-up visits from medical records as follows: heart rate (or pulse rate), systolic BP, diastolic BP, body temperature °C), respiratory rate.

### Hematology

Hematology lab tests will be collected from the medical records at baseline and every other day through treatment and hospital stay (as applicable).

The follow hematology labs are tested: white cell count, red blood cell count, hemoglobin, hematocrit, mean cell volume (MCV), mean cell hemoglobin (MCH), mean cell hemoglobin concentration (MCHC), platelets, neutrophils, lymphocytes, monocytes, eosinophils, and basophils.

### Serum Biochemistry

Biochemistry lab tests will be collected from the medical records at baseline and every other day through treatment and hospital stay (as applicable). In the case of a clinically significant abnormal lab result, continue to collect and test those samples to follow subject to resolution and/or discharge, whichever should occur first.

The following biochemistry lab tests are tested: sodium, potassium, chloride, bicarbonate, urea, creatinine, glucose, total calcium, phosphate, ferritin, high-sensitivity C-reactive protein (hs-CRP), protein, albumin, globulins, total bilirubin, alkaline phosphatase (ALP), alanine aminotransferase (ALT), aspartate aminotransferase (AST) and lactate dehydrogenase (LDH).

### Cytokine and Chemokine Assays

Cytokine and chemokine assay lab test results will be collected and recorded before the first treatment, after the last treatment, and at hospital discharge. A cytokine panel is tested to include, but not limited to: Tumor Necrosis Factor alpha (TNF $\alpha$ ), interferon gamma (IFN $\gamma$ ), Interleukin 1 beta (IL-1 $\beta$ ), interleukins (IL-6, IL-8, IL-10, IL-12). Data is reported for research purposes, and the sample is destroyed after data is collected.

### Ordinal Scale for Clinical Improvement

The clinical status will be recorded at every visit from baseline to Day 60 using the World Health Organization (WHO) “Ordinal Scale for Clinical Improvement”. This 8-point ordinal scale was created to be responsive to the eligible patient population, intervention, and course of illness of COVID-19. The score should reflect the highest level of support the subject required on the day being recorded. The following is scores are collected:

Score	Descriptor
0	No clinical or virological evidence of infection
1	No limitation of activities
2	Limitation of activities
3	Hospitalized, no oxygen
4	Hospitalized, oxygen by mask or nasal prongs
5	Hospitalized, non-invasive ventilation or high-flow oxygen
6	Hospitalized, mechanical ventilation
7	Hospitalized, ventilation + additional organ support – pressors, RRT, ECMO
8	Death

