## 1.2 Schedule of Assessments (SoA)

Visits will be conducted as described:

	Screen	Treatment					Hospitalization	Follow-up	
		1 	2	3	4	5		28	60
Study Day	-3 to Baseline						Every day until discharge		
Visit Window (± days)	--	--	--	--	--	--	--	3	3
COVID-19 diagnosis	X								
Informed consent	X								
Medical history and pre-existing conditions	X								
Inclusion/exclusion criteria	X	X							
Urine pregnancy test		X							
Demographics		X							
Randomization		X							
Treatment (active or placebo)		X	X	X	X	X			
Vital signs		X	X	X	X	X	X		
Blood oxygen saturation		X	X	X	X	X	X		
ECG (telemetry) 		X	X	X	X	X	X 		
Hematology 		X		X		X	X 		
Biochemistry 		X		X		X	X 		
Cytokine/chemokine assay 		X				X	X 		
Mortality							X	X	X
Ordinal scale for clinical status		X	X	X	X	X	X	X	X
NEWS2 score		X	X	X	X	X	X	X	X
Hospital LOS and ICU LOS		X	X	X	X	X	X	X	X
Date of intubation/extubation, days on ventilation			X	X	X	X	X	X	X
Concomitant medications		X	X	X	X	X	X	X	X
Adverse events		X	X	X	X	X	X	X	X

 Day 1 baseline assessments occur before the first dose of treatment; pregnancy test to be conducted as applicable.

 Telemetry or 12 ECG lead monitored once daily.

 Hematology and biochemistry tests are performed at baseline and every other day through hospitalization.

 Cytokine and chemokine assays are collected at baseline before treatment, at Day 5 after treatment, and at discharge.

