## 5 STUDY PLAN, PROCEDURES, AND ASSESSMENTS

### 5.1 Description of Study Visits

The mortality, clinical effects, safety, and tolerability of treatment will be evaluated from baseline through Day 60. Evaluations at screening and during the 5-day treatment occur in person. Evaluations after the 5-day treatment to the end of the study (days 6 to 60) will typically occur via telephone. The Schedule of Assessments is shown in [Section 1.2](#).

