#### **5.1.5 Post-Treatment Follow-Up (Days 28, 60)**

The following procedures will be performed at all follow-up visits (Days 28, 60):

- Mortality
- Concomitant medications/therapies
- Hospital LOS
- ICU LOS
- Ordinal scale and NEWS2 assessments
- Aes

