## 9.4 Study Endpoints

### 9.4.1 Primary Endpoint

The primary endpoint assesses the effect of Ampion compared to placebo on clinical improvement. Clinical improvement is measured as the change in ordinal scale from baseline through Day 5 and Day 28.

Let  $\mu_A$  and  $\mu_S$  represent the mean changes in the ordinal scale for Ampion and control respectively. Then, it is desired to demonstrate that the mean change for Ampion is different than the corresponding mean change for the control, respectively. Formally, this is presented as:

$$H_0: \mu_A = \mu_S \quad \text{versus} \quad H_A: \mu_A \neq \mu_S$$

The difference between Ampion and Placebo with respect to the change from baseline at Day 5 and Day 28 will be tested utilizing a Wilcoxon rank-sum test. To assess any potential time trends, an exploratory repeated measures analysis of variance will be performed with terms for treatment, time, and the interaction between the two.

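### At Day 28, scores 0 and 1 of the primary ordinal scale differ by virological evidence that the plan does not schedule, so for a fully recovered patient the choice is left to site convention

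*Protocol*

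**What the plan says.** - **Scale.** Protocol 5.2 (Ordinal Scale for Clinical Improvement) lists scores 0 to 8. Score 0 is "No clinical or virological evidence of infection" and score 1 is "No limitation of activities".
- **Scoring rule.** The only instruction is "The score should reflect the highest level of support the subject required on the day being recorded".
- **Timing.** "The clinical status will be recorded at every visit from baseline to Day 60". Protocol 5.1.5 lists "Ordinal scale and NEWS2 assessments" at Days 28 and 60, with mortality, medications, lengths of stay and adverse events. It lists no swab.
- **Contact.** "Evaluations after the 5-day treatment to the end of the study (days 6 to 60) will typically occur via telephone" (Protocol 5.1). The synopsis gives Days 28 and 60 as telephone visits.
- **Virology.** The Schedule of Assessments has one relevant row, "COVID-19 diagnosis", marked at screening only. The later laboratory work is hematology, biochemistry and cytokines.
- **Analysis.** "Clinical improvement is measured as the change in ordinal scale from baseline through Day 5 and Day 28" (Protocol 9.4.1). Protocol 9.4.1 and SAP 4 apply a Wilcoxon rank-sum test to change on the full scale. Neither document combines 0 and 1 or says how to choose between them without a test. The missing-score rule (Protocol 9.5, SAP 8.1) covers unreachable patients only.

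**The concern.** Take a patient who went home, has no symptoms and is back to normal activity. A telephone call can establish all of that. It cannot establish virological status unless a test happens to have been done outside the trial. One site may enter 0 because nothing points to infection; another may enter 1 because there is no negative test. Both follow the protocol.

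The primary analysis ranks these two entries differently. With about 20 sites, part of the Day 28 primary score may reflect recording habit rather than clinical state, and a one-point difference between recovered patients would have no clear meaning. Whether this also costs power depends on how many patients reach this state and on how varied the baseline scores are.

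**Working it through.** **1. The plan's own power figure.** The only one is at least 80% for Day 28 mortality of 8% versus 26% with 100 per arm (Protocol 4.1 and 9.1, SAP 2.4). With a pooled z test at two-sided 0.05:

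(0.18 − 1.96 × √(2 × 0.17 × 0.83/100)) / √((0.26 × 0.74 + 0.08 × 0.92)/100) = (0.18 − 0.1041)/0.0516 = 1.47, so power is 92.9%. At the final alpha of 0.047 it is 92.6%.

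The statement is true as a lower bound, but it concerns mortality. The documents give no power figure for the ordinal score, so the rest is illustrative.

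**2. Can any rule in the documents separate 0 from 1?**

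| Source | Does it separate them for a symptom-free, unrestricted patient at home? |
|---|---|
| Support-based scoring rule | No: neither state involves support |
| Symptoms asked by telephone | No: they keep a symptomatic patient out of 0, but this patient has none |
| Scheduled viral test after screening | None exists |
| Missing-score rule | No: the score is not missing |

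**3. How many patients could be affected?** Assume that 40% or 60% of controls are recovered without limitation at Day 28, with a common odds ratio of 2.2.
- 40%: odds 0.667 × 2.2 = 1.467, so 59.5% on Ampion; 40 + 59.5 ≈ 99 of 200 patients.
- 60%: odds 1.5 × 2.2 = 3.3, so 76.7% on Ampion; 60 + 76.7 ≈ 137 of 200 patients.

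**4. Why power can fall.** If everyone starts at score 4 and 0 and 1 are pooled, two recovered patients tie. The share of between-arm pairs that tie this way is 0.595 × 0.40 = 24%, or 0.767 × 0.60 = 46%. If 0 or 1 is entered by fair coin, half of those pairs (12% or 23%) are decided at random. This adds variance and no signal.

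**5. Why mixed baselines remove the loss.** Change is Day 28 score minus baseline. From baseline 4, a score of 1 gives −3 and a score of 0 gives −4. From baseline 5, a score of 1 also gives −4. Recovered patients with different baselines are therefore already spread over several change values before any 0/1 ambiguity arises.

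**6. Simulation.** Inputs from the documents: 100 per arm, two-sided alpha 0.047, Wilcoxon test on change from baseline. Assumed inputs: recovered share as in step 3, 15% control deaths, the remaining controls spread over the intermediate levels, odds ratio 2.2, Day 28 outcome unrelated to baseline, recovered patients given 0 or 1 by fair coin. There were 3,000 trials per setting. The pooled level is analysed as 1.

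| Baseline mix | Controls recovered | Power, 0/1 pooled | Power, 0/1 split | Change |
|---|---|---|---|---|
| All at 4 | 40% | 83% | 79% | −4 |
| All at 4 | 60% | 73% | 60% | −13 |
| 90/7/3% at 4/5/6 | 40% | 79% | 76% | −3 |
| 90/7/3% at 4/5/6 | 60% | 66% | 59% | −7 |
| 5/80/10/5% at 3/4/5/6 | 40% | 75% | 75% | 0 |
| 5/80/10/5% at 3/4/5/6 | 60% | 59% | 55% | −4 |
| 5/65/25/5% at 3/4/5/6 | 40% | 71% | 73% | +2 |
| 5/65/25/5% at 3/4/5/6 | 60% | 53% | 54% | +1 |

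Variations:
- If a worse baseline predicts a worse outcome, mixed baselines lose about 0 to 6 points.
- If 85% of recovered patients are coded the same way, the losses with all baselines at 4 shrink to about 2 points (40% recovered) and 7 points (60%).
- At 20% recovered, even all baselines at 4 lose nothing (86% versus 86%).
- Coding that is consistent within each of 20 sites but differs between sites gives similar results.

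**7. Type I error.** With no treatment effect and baselines of 70/25/5% at 4/5/6, rejection rates were 0.040 to 0.056 pooled and 0.038 to 0.058 split. The nominal level is 0.047 and the Monte Carlo standard error about 0.005 (2,000 trials per setting). Splitting shows no inflation.

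**The case against.** The strongest reply is that this is a small coding ambiguity in a scale the protocol takes from WHO.

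- **Score 0 can be read as absence of evidence.** A well patient with no positive test arguably qualifies, so it goes too far to say that a site cannot assign 0. That reading is reasonable, but the protocol does not adopt it, and sites may differ.
- **The larger power losses need near-uniform baselines.** Protocol 4.4 admits patients on high-flow oxygen, non-invasive ventilation or mechanical ventilation (scores 5 and 6), and Protocol 3.4 stratifies on severe versus critical disease. This stands: 13 points is an upper end, not an expectation. With a broad mix, pooling brings no power and in some settings costs a point or two.
- **The recovered share has no source.** A reader might infer from the Phase I mean stays of 7 and 11 days (Protocol 2.3) that this is the largest group at Day 28. Length of stay shows discharge, which covers scores 0, 1 and 2. It says nothing about limitation of activities, and Phase I had 27 subjects. The share remains an assumption.
- **Bias.** A reader might infer a distorted treatment comparison or a false positive risk. Assessors are blinded (Protocol 3.4), so miscoding should not depend on arm, and the rejection rates stay near nominal.
- **A virological claim.** A reader might infer that the trial would claim viral clearance. The stated endpoint is clinical improvement, so the documents do not support this.

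What survives is that the protocol asks sites to make a distinction for which it schedules no evidence and gives no rule, and that the primary test uses the answer.

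**Conclusion.** The point holds as a matter of noise and interpretability in the Day 28 component of the primary endpoint. For symptom-free, unrestricted patients at home, 0 versus 1 rests on convention. The power cost lies between about zero (mixed severe and critical baselines) and about 13 points (nearly all patients at score 4 and 60% of controls recovered), and it is smaller if sites mostly code alike. This range rests on an assumed odds ratio of 2.2, 15% control deaths and random coding; the documents do not fix the baseline mix or the recovered share.

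Day 5 is barely touched, because patients still in hospital score 3 or higher. The case for acting does not depend on the power figure: the distinction cannot be verified from the scheduled data, and a choice made after unblinding would count as post hoc under SAP 1.

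**What to change.** - In Protocol 9.4.1 and SAP 4, state before unblinding that scores 0 and 1 form one level for the primary change-from-baseline analysis. State the numeric value given to that level (1 in the calculations above), because the change score depends on it.
- Use the same scale at Day 5 and Day 28, and in the interim test (Protocol 9.2.3, SAP 7.1), which repeats the primary test.
- Keep recording the scale as it is, with no instruction to enter a particular code at telephone visits. Such an instruction would make the raw 0 and 1 counts meaningless.
- Report the unpooled scale as a sensitivity analysis, with raw counts of 0 and 1 by arm.

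The cost is a wording change and slightly more analysis. The analysed scale has eight levels instead of the nine listed, so it no longer matches the published scale exactly; the sensitivity analysis covers that. No visit, sample or test is added.

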### NEWS2 Score for Determining the Degree of Illness

In March 2020, the WHO recommended the NEWS2 scoring system as a possible tool for medical early warning scores for COVID-19 patients (WHO Guidance, 2020). Initially, the National Institute for Health and Care Excellence (NICE) recommended the NEWS2 scoring system in their 2020 guidance, however it was removed from their 2021 guidance. In a letter to the editor in the European Journal of Internal Medicine in December 2020, Rigoni et al. indicate that there is still limited direct evidence on the performance of NEWS2, however a hypothesis remains that NEWS2 may be a valuable tool in treating COVID-19 patients. The NEWS2 will be calculated using the oxygenation requirement (room air or supplemental oxygen), SpO2 level, and vitals (body temperature, respiratory rate, heart rate and blood pressure) collected during study visits. The NEWS2 score is recommended by the National Institute for Health and Care Excellence (“NICE”) for managing COVID-19 patients.

### Adverse Events

Any documented adverse event. These include but are not limited to the following: cardiac injury, arrhythmia, septic shock, liver dysfunction, acute kidney injury, and multi-organ failure.

## 6 DISCONTINUATION CRITERIA

### 6.1 Early Discontinuation of the Study

Discontinuation or temporary suspension is allowed for any reason. The Sponsor may suspend or terminate the study due to the development of any new or unexpected life threatening or adverse events, prolonged hospitalization, or other potential grounds for stopping the study. The number of subjects, as well as the types and the grade severity of the adverse events (according to Common Terminology Criteria for Adverse Events (CTCAE)) may trigger the temporary suspension of study product administration pending a safety investigation as follows:

If any reactions of grade 3 and above (as defined using the CTCAE grading scale version 5.0 or newer) are observed in any patient within 24 hours of product administration, a safety investigation will occur, which may trigger the temporary suspension of study product administration.

It is agreed that for reasonable cause, either the investigator or the Sponsor may terminate this study, provided written notice is submitted at a reasonable time in advance of intended termination; if by the investigator notice is to be submitted to Ampio Pharmaceuticals, Inc., and if by the Sponsor, notice will be provided to each investigator.

If a severe local reaction or drug-related SAE occurs at any time during the study, the DSMB will review the case immediately.

The study will be immediately suspended and no additional Ampion treatments administered pending review and discussion of all appropriate study data by the DSMB if one or more participants develop any of the following adverse events deemed to be possibly, probably, or definitely related to Ampion by the Investigator and/or Medical Monitor, based upon close temporal relationship or other factors:

- Death
- Respiratory deterioration requiring extracorporeal membrane oxygenation (ECMO)
- Anaphylaxis
- Acute adverse reaction at administration of treatment (i.e., sudden change in vital signs)

The study will not be restarted until all parties have agreed to the course of action to be taken and the IRB/EC has been notified.

### 6.2 Early Discontinuation of Individual Participants

Discontinuation of individual participants is allowed for any reason. Evaluations of participants who discontinue the study early are described in the Schedule of Assessments in [Section 1.2](#).

## 7 TREATMENT

All participants will receive the standard of care for COVID-19. Participants randomized to the active arm will receive Ampion through nebulized inhalation daily for 5 days. Participants randomized to the control arm will receive placebo through nebulized inhalation daily for 5 days.

Patients will be allocated to a sequentially numbered treatment in accordance with the randomization schedule following confirmation of eligibility and before treatment.

### 7.1 Dosing and Administration of Study Medication

Ampion treatment will be provided as a solution in glass vials ready for human use and treatment administration. Appropriately trained site personnel will administer the study treatment.

Participants will receive a daily dose (32 mL/day) of study intervention (active or placebo) through nebulized inhalation delivered in four equally divided doses of 8 mL, every 6 hours (q\_6), for 5 days. Treatment should commence within 6 hours of randomization. Treatment should terminate at the end of the 5-day treatment period, or when a patient is discharged, whichever comes first.

As outlined in [Section 2.1](#), Ampion or placebo will be delivered in nebulized form to patients using the Aeroneb® Solo Nebulizer System (manufacturer Aerogen Limited, Galway, Ireland), which consists of the Aerogen® Pro-X Controller and the Aerogen® Solo adaptor. Study intervention (active or placebo) aerosolized using the Aeroneb® Solo Nebulizer will be delivered *via* an appropriate aerosol delivery assembly for inhaled drug administration as clinically indicated, *e.g.*, using the hand-held Aerogen Ultra, NIV, and/or a mechanically ventilated circuit. The aerosol delivery assembly used to deliver aerosolized Ampion to each patient will be determined at the treating physician's discretion based on the severity of respiratory illness and clinical needs of the patient at enrolment and continuing throughout the study. Appropriate settings for aerosol delivery assembly respiratory parameters (*e.g.*, supplemental O2 content, flow rate, inspiratory/expiratory pressure, etc.) will be determined for each patient by the treating physician on an ongoing basis as clinically indicated.

Participants will be monitored for any respiratory and/or cardiac distress via vital sign monitoring including respiratory rate, heart rate, and blood pressure daily throughout the study product treatment period.

### 7.2 Study Medication Storage and Accountability

Investigational product (active and placebo) should be stored at room temperature (59° – 77°F or 15° – 25°C) in a secure area with restricted access. The Investigator, the clinical site pharmacist, or other personnel authorized to store and dispense investigational product is responsible for ensuring that the investigational product used in the clinical study is securely maintained as specified by the Sponsor and in accordance with the applicable regulatory requirements.

All investigational product is to be dispensed in accordance with the Investigator's prescription.

It is the Investigator's responsibility to ensure that an accurate record is maintained of investigational product issued. All investigational product not used during the study must be returned to Ampio Pharmaceuticals Inc., or designated representative after study completion.

If any quality issue is noticed upon the receipt or use of an investigational product (i.e., deficiencies in condition, packaging, appearance, associated documentation, labeling, expiry date, etc.), Ampio Pharmaceuticals, Inc. must be promptly notified.

Under no circumstances may the Investigator supply investigational product to a third party, allow the investigational product to be used other than as directed by this clinical study protocol, or dispose of investigational product in any other manner.

